## 7.2 SERIOUS ADVERSE EVENTS

### 7.2.1 DEFINITION

A serious adverse event (SAE) is any adverse event (experience) that in the opinion of either the investigator or sponsor results in **ANY** of the following:

- Death.
- A life-threatening adverse event (experience). Any AE that places a subject or subject, in the view of the Investigator or sponsor, at immediate risk of death from the reaction as it occurred. It does **NOT** include an AE that, had it occurred in a more severe form, might have caused death.
- Inpatient hospitalization or prolongation of existing hospitalization (for > 24 hours).
- A persistent or significant incapacity or substantial disruption of the ability to conduct normal life functions.
- A congenital anomaly or birth defect.
- Important Medical Event (IME) that, based upon medical judgment, may jeopardize the subject or subject and may require medical or surgical intervention to prevent one of the outcomes listed above.

Elective hospital admission (including planned treatment for progressive disease or a planned protocol procedure), admission for socioeconomic reasons, and death due to tumor progression will not be considered an SAE.

All SAEs will be collected from the date of subject or subject signing consent until 30 days after the last dose of study drug and/or procedure.

### **7.2.2 REPORTING SERIOUS ADVERSE EVENTS**

AE may be identified as an Unanticipated Problem by the Investigator. Please refer to **Section 7.3.2** for details on reporting Unanticipated Problems.

The SAE Form should be completed with all available information, including a brief narrative describing the adverse event and any other relevant information. If applicable, the narrative must also include identification of similar reports and an analysis of the significance of the AE.

### **7.2.3 FOLLOW-UP FOR SERIOUS ADVERSE EVENTS**

All SAEs will be followed until resolution, stabilization, death, or the start of new treatment.

## **7.3 UNANTICIPATED PROBLEMS**

### **7.3.1 DEFINITION**

An Unanticipated Problem (UP) is any incident, experience, or outcome that meets all of the following criteria:

- Unexpected (in terms of nature, severity, or frequency) given:
  - The research procedures that are described in the study-related documents, including study deviations, as well as issues related to compromise of subject privacy or confidentiality of data.
  - The characteristics of the subject population being studied.
- Related or possibly related to participation in the research (possibly related means there is a reasonable possibility that the incident, experience, or outcome may have been caused by the procedures involved in the research).
- Suggests that the research places subjects or others at a greater risk of harm (including physical, psychological, economic, or social harm) than was previously known or recognized and if in relation to an AE is also deemed **Serious** per **Section 7.2**.

### **7.3.2 REPORTING UNANTICIPATED PROBLEMS**

SAEs that are serious, unexpected and for which there is a reasonable possibility that the study drug caused the adverse event are reported on the Unanticipated Problem Form and submitted to CRS Compliance Office within 24 hours of becoming aware of the Unanticipated Problem.

Within 5 business days, an Unanticipated Problem Form should be completed with all available information, including a brief narrative describing the unanticipated problem and any other relevant information.

Within 5 business days of becoming aware of new information about the Unanticipated Problem, submit this updated information to CRS Compliance with an updated UP Form.

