### 4.2 STUDY METHODS

During the course of treatment for peritoneal carcinomatosis while the patient is under anesthesia, CRS-HIPEC will be performed. Surgical exposure is performed through a midline incision and the assistance of retractors as shown in the technical schema (Appendix D).

The IVM technology utilized at Mayo Clinic currently consists of a high resolution confocal endomicroscope (Appendix E). This apparatus has the ability to provide single cell resolution and high quality images of the microvasculature. While the typical application of this device is to investigate GI mucosal surfaces (i.e. esophagus or colon), it can be readily and easily applied to any surface. It can be sterilized or used with a sterile sleeve in order to interface with the peritoneal surface.

The microscope will be moved into position next to the OR table by the operating surgeon. The microscope will be covered with a standard sterile drape similar to that used for cords associated with other intraoperative devices (NeoProbe or intraoperative ultrasound). The only exposed area will be the microscopic objective located at the tip of the endoscope, which will be made sterile. This microscopic objective will come into close contact with the peritoneal surface for microscopic observation. Once the microscopic objective is in proper position, the epifluorescent light source will be turned on and digital video recording will commence. All video images will be captured to the hardware directly attached to the microscope (Appendix E). All data will be backed up on a password-protected hard drive in the Principal Investigator's laboratory.

Following several observations over various portions of the peritoneal surface, 1 ampule (5 mL) 25% fluorescein will be injected intravenously and observation will continue until loss of

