## 7 SAFETY EVALUATION

### 7.1 ADVERSE EVENTS

#### 7.1.1 DEFINITION

An adverse event or adverse experience (AE) is any untoward medical occurrence associated with the use of a drug in humans, whether or not considered drug related. Therefore, an AE can be **ANY** unfavorable and unintended sign (including an abnormal laboratory finding), symptom, or disease temporally associated with the use of a medicinal (investigational) product, whether or not considered related to the medicinal (investigational) product (attribution of ‘unrelated’, ‘unlikely’, ‘possible’, ‘probable’, or ‘definite’).

An AE is considered “unexpected” if it is not listed in the investigator brochure or is not listed at the specificity or severity that has been observed; or if an investigator brochure is not required or available, is not consistent with the risk information described in the general investigational plan in other study-related documents. “Unexpected” also refers to adverse events that are mentioned in the investigator brochure (or other study-related documents) as occurring with a class of drugs or as anticipated from the pharmacological properties of the drug, but are not specifically mentioned as occurring with the particular study drug.

Adverse events will be recorded in this study for the purpose of safety monitoring and adverse events are anticipated to be absent or unlikely.

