#### 7.1.2 GRADING AND RELATIONSHIP TO DRUG

The descriptions and grading scales found in the CTEP Version 4 of the NCI Common Terminology Criteria for Adverse Events (CTCAE) will be utilized for AE reporting. CTEP Version 4 of the CTCAE is identified and located at: [http://ctep.cancer.gov/protocolDevelopment/electronic\\_applications/ctc.htm](http://ctep.cancer.gov/protocolDevelopment/electronic_applications/ctc.htm). AEs not covered by

specific criteria should be reported with common medical terminology and graded according to definitions provided in the CTCAE Version 4.

AEs NOT listed in the NCI-CTCAE, the severity of AEs will be graded as follows:

- **Grade 1 – Mild:** Event barely noticeable to subject; no limitation in activity, no minimal medical intervention/therapy required.
- **Grade 2 – Moderate:** Event of a sufficient severity to make participant uncomfortable. ADL limited; no or minimal medical intervention/therapy required.
- **Grade 3 – Severe:** Event causes significant discomfort/limitation in activity. May be such severity that the subject cannot continue on study. Severity may cause cessation of treatment. Treatment for symptoms may be given and/or subject hospitalized.
- **Grade 4 - Life Threatening:** Event places the participant at immediate risk of death from the reaction as it occurred. Significant medical intervention/therapy required; hospitalization or hospice care probably.
- **Grade 5 - Death.**

The relationship of event to study drug will be documented by the Investigator as follows:

- **Unrelated:** The event is clearly related to other factors such as the subject's clinical state, other therapeutic interventions or concomitant drugs administered to the subject.
- **Unlikely:** The event is doubtfully related to investigational agent(s). The event was most likely related to other factors such as the subject's clinical state, other therapeutic interventions, or concomitant drugs.
- **Possible:** The event follows a reasonable temporal sequence from the time of drug administration, but could have been produced by other factors such as the subject's clinical state, other therapeutic interventions or concomitant drugs.
- **Probable:** The event follows a reasonable temporal sequence from the time of drug administration, and follows a known response pattern to the study drug. The event cannot be reasonably explained by other factors such as the subject's clinical state, therapeutic interventions or concomitant drugs.

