- **Definite:** The event follows a reasonable temporal sequence from the time of drug administration, follows a known response pattern to the study drug, cannot be reasonably explained by other factors such as the subject's condition, therapeutic interventions or concomitant drugs; AND occurs immediately following study drug administration, improves upon stopping the drug, or reappears on re-exposure.

A suspected adverse reaction is any AE for which there is a reasonable possibility that the drug caused the adverse event. Reasonable possibility means there is evidence to suggest a causal relationship between the drug and the adverse event, such as:

- A single occurrence of an event that is uncommon and known to be strongly associated with drug exposure (e.g., angioedema, hepatic injury, Stevens-Johnson Syndrome).
- One or more occurrences of an event that is not commonly associated with drug exposure, but is otherwise uncommon in the population exposed to the drug.
- An aggregate analysis of specific events observed in a clinical research study that indicates those events occur more frequently in the drug treatment group than in a concurrent or historical control group.

An AE for which there is a reasonable possibility that the drug caused the adverse event includes those assessed as having a Possible, Probable, or Definite causality assessment.

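### Serious, unexpected harm clearly due to the endomicroscope can be an Unanticipated Problem under 7.3.1 without triggering the mandatory 24-hour report in 7.3.2

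*Combined protocol and SAP*

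**What the plan says.** Section 7.3.1 sets out what makes an event an Unanticipated Problem (UP). It must be unexpected, at least possibly related to taking part in the research, and a sign of more risk than was known. If it is an adverse event, it must also be serious. Possible relatedness means that "there is a reasonable possibility that the incident, experience, or outcome may have been caused by the procedures involved in the research".

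Section 7.3.2 holds the reporting duty. It states that "SAEs that are serious, unexpected and for which there is a reasonable possibility that the study drug caused the adverse event are reported" on the UP Form, which goes to the compliance office "within 24 hours of becoming aware of the Unanticipated Problem". Two further sentences ask for a fuller form within 5 business days and for updates on the same clock.

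Section 7.1.2 supplies the only causality scale: "The relationship of event to study drug will be documented by the Investigator as follows". Its lowest level, Unrelated, reads "The event is clearly related to other factors such as the subject's clinical state, other therapeutic interventions or concomitant drugs administered to the subject". Events with a reasonable possibility of drug causation are said to be a group that "includes those assessed as having a Possible, Probable, or Definite causality assessment". The adverse event definition in Section 7.1.1 is also framed on a drug: "An adverse event or adverse experience (AE) is any untoward medical occurrence associated with the use of a drug in humans".

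The study intervention is more than the dyes. Section 4.2 says of the endomicroscope: "This microscopic objective will come into close contact with the peritoneal surface for microscopic observation". The same section has the peritoneum viewed several times before fluorescein is injected, with ICG following later.

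**The concern.** The definition and the reporting trigger, in adjacent subsections, use different tests of causation. One asks about the research procedures and the other about the study drug. The endomicroscope falls between them.

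It is also the component with the least prior experience in this setting. Section 4.2 gives its usual application as gastrointestinal mucosa, and Section 1 says intravital microscopy has not been studied in human peritoneal carcinomatosis. The risk statements in Sections 1.3 and 1.5 cover the dyes and the background surgery and name no device risk, so serious scope-related harm would probably count as unexpected. At stake is whether such an event must reach the compliance office promptly, and whether it has its own place in the adverse event summary planned in Section 9.

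**Working it through.** No arithmetic applies, so the check is to take four kinds of serious, unexpected event through the rules as written. It is assumed throughout that the event also suggests more risk than was known, as 7.3.1 requires.

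| Event | UP under 7.3.1? | Grade under 7.1.2 | 24-hour trigger in 7.3.2 met? |
|---|---|---|---|
| Reaction to a dye | Yes | Possible or higher | Yes |
| Harm after a dye, cause unclear | Yes | Could be Possible, on timing | Yes, if so graded |
| Harm after a dye, clearly due to the scope | Yes | Unrelated | No |
| Scope harm before either dye is injected | Yes | Unrelated, at most Unlikely | No |

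The last row follows in three steps.

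1. Possible, Probable and Definite each require a reasonable time sequence from drug administration. Harm that occurs before the intravenous dyes has none, so only Unrelated or Unlikely is open.
2. Section 7.1.2 links a reasonable possibility of drug causation to Possible, Probable and Definite. Unrelated and Unlikely are not listed.
3. The drug condition in the first sentence of 7.3.2 therefore fails, although the event may have been caused by a research procedure and so satisfies 7.3.1.

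The third row rests on the wording of Unrelated. Its examples of other factors are introduced by *such as*, so the list is open. The scope is not obviously a therapeutic intervention, but it is a factor other than the drug.

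Other provisions that might close the gap:

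- Section 7.1.3 requires every grade at every attribution level to be recorded. Section 6.2 starts recording at entry to the operating room, which covers the period before the dyes.
- Section 7.2.1 collects serious events until 30 days after the last dose or procedure. Section 11.1 puts them on the Serious Adverse Event Form, handled as expedited, but gives no clock or recipient.
- Section 7.2.2 lets the investigator identify an event as a UP. This is optional, and it refers the reader back to 7.3.2.
- Section 8 has the monitoring board review the study annually. At the Section 9 rate of one subject per month, the 10 patients of Part I take 10 ÷ 1 = 10 months, so all could be observed before a first review at 12 months.

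These provisions secure the record of the event. None makes a 24-hour submission mandatory for it.

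**The case against.** The strongest reply is that little is lost. Section 7.3.1 is a definition and orders no report. The 5-business-day and update sentences in 7.3.2 do not repeat the drug condition, so an event that meets the definition arguably still has a UP Form route. All adverse events are documented whatever their cause, serious ones get a form with a narrative, and the complication rates planned in Section 9 are not limited to drug-related events. Section 4.2 also describes a sterile drape and tip, and expects the whole observation to take 15 to 20 minutes without notably lengthening surgery.

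Most of this stands, and it rules out several stronger readings.

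- A reader might infer that device harm escapes reporting altogether. It does not; what is missed is the mandatory 24-hour step.
- A reader might infer that all scope harm will be coded Unrelated. That follows only where the cause is clear or the harm precedes the dyes. Ambiguous harm afterwards can be graded Possible.
- A reader might infer that no device-related rate can be estimated. Events could be counted afterwards from the records and narratives. What is lacking is a prespecified attribution.
- A reader might want separate attribution for each dye. Nothing in the documents requires it, and the case report form is not among them.

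The reply does not remove the conflict itself. The longer clock is slower, its independence from the sentence before it is a matter of interpretation, and the investigator's route is discretionary.

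**Conclusion.** The point holds in a limited form. Sections 7.3.1 and 7.3.2 apply different causation tests. As a result, serious, unexpected harm clearly due to the endomicroscope or the observation can be a UP without triggering the 24-hour submission. The clearest case is harm before either dye is injected.

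This rests on two readings: that Unrelated and Unlikely do not amount to a reasonable possibility of drug causation, and that the drug condition in 7.3.2 means what it says. The passage in 7.1.2 says *includes*, so the first is the natural reading rather than an explicit exclusion.

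The effect has no numerical size. The rule applies to all of up to 30 patients, but the documents give no expected frequency of scope-related harm, and the precision of a zero count in 30 patients would not measure the defect. The primary endpoint and the decision to proceed to Part II are unaffected. The issue is prompt safety reporting for the procedure under test.

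**What to change.** In Section 7.3.2, widen the trigger from events that the study drug may have caused to events that *a study drug, the study device or a research procedure* may have caused, so that it matches 7.3.1.

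In Section 7.1.2, add a separate relationship assessment for the endomicroscope and observation procedure on the existing five-level scale, and state that Possible or higher on either assessment counts as a reasonable possibility. Device- or procedure-related events then have a prespecified attribution for the Section 9 adverse event summary.

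The cost is protocol wording, one added attribution item on the adverse event form and possibly a few more expedited reports. Treatment, sample size and the planned analyses do not change.

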## 8 DATA AND SAFETY MONITORING

The Mayo Clinic Data and Safety Monitoring Board will assess the progress of the study, the safety data, and critical efficacy endpoints. The DSMB will review the study annually and will make recommendations that include but not limited to; (a) continuation of the study, (b) modifications to the design (c) or termination of the study.

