## 9 STATISTICAL METHODOLOGY

Initially ten patients will be treated to determine the feasibility of HIVM for peritoneal carcinomatosis. This first part of the study is a pilot study of feasibility. If seven or more patients are deemed a success by meeting all of the criteria below, then HIVM will be deemed feasible in the study of peritoneal carcinomatosis. Criteria include the ability to complete each of the following:

1. Identify and measure vessels associated with peritoneal tumor implants
2. Determine vessel density per 10x field
3. Visualize vital dyes within the vessels [fluorescein and indocyanine green (ICG)]
4. Calculate the blood flow velocity of the vessels and tissue penetration of fluorescein and ICG as markers of vessel permeability.

If the true success rate is 60%, the probability of deeming HIVM feasible is 63%; if the true success rate is 70%, then the probability of deeming HIVM feasible is 88%; and if the true success rate is 90%, then the probability of deeming HIVM feasible increases to 99%.

If HIVM is deemed feasible, then an additional 20 patients will be accrued to this study in order to address the following:

1. Post-operative comparison of the microvasculature of peritoneal carcinomatosis with normal tissue (peritoneum) in each individual subject using vessel diameters, vessel density, detection of intravital dye and flow rates.
2. Post-operative correlation of the microvasculature with pathologic features of the tumor implants (i.e. tumor grade) at the time of the final pathology report (5-7 days after surgery).
3. Post-operative correlation of the microscopic observation of the tumor microvasculature tumor-specific and overall survival.

An abnormal HIVM observation is defined by any of the following criteria:

1. Aberrant vessel structure compared to normal tissue, which includes tortuosity of the vessel wall or a closed loop formation.
2. Aberrant vessel branching patterns compared to normal tissue, which includes erratic and disorganized branching points.
3. Blood vessel density that is less than or greater than one standard deviation of the blood vessel density observed in normal tissue.
4. Inability to detect flow or intravital dye within a vessel.
5. Average blood flow rate through observed vessel that is less than one standard deviation of the average blood flow rate through a normal vessel.

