A matched analysis will be performed for observations of microvasculature between the peritoneal tumor implants and normal tissue. For dichotomous variable comparisons between vessel structure (normal vs aberrant), vessel branching patterns (normal vs aberrant), or detection of intravital dye (present vs absent), a McNemar's test will be performed. For continuous variable comparisons between blood vessel density and average blood flow rate, a paired t test will be performed.

Associations between characteristics for the baseline (normal peritoneal microvasculature observed surrounding the tumor implant site) and tumor implant itself will be depicted with graphics, correlations, and model results.

Adverse event and complication rates will be described using upper one-sided 95% Clopper Pearson confidence limits.

Overall survival will be defined as the duration of time from diagnosis to time of death. Disease specific survival will be defined as the time from CRS-HIPEC to death due to recurrence. Overall survival and disease specific survival will be generated using standard Kaplan-Meier methodology.

A maximum of 30 subjects will be enrolled in this study (initially 10 to determine feasibility and then 20 additional subjects if deemed feasible). The accrual rate is estimated at one subject per month, and the estimated study duration is 30 months.

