## 14 APPENDICES

### Appendix A: Fluorescein Drug Package Insert.

- AK-FLUOR® (fluorescein injection, USP) is a sterile solution for use intravenously as a diagnostic aid
- Indicated in diagnostic fluorescein angiography or angioscopy of the retina and iris vasculature
- Meets strict USP quality standards
- AK-FLUOR® is contraindicated in patients with known hypersensitivity to fluorescein sodium or any other ingredients in this product
- Rare cases of death due to anaphylaxis have been reported [see *Warnings and Precautions (5.1)* and *Adverse Reactions (6.2)*]
- Available direct or through your authorized wholesaler or distributor

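### Part II opens on the imaging count alone, and no text brings a safety review or a serious dye reaction to the DSMB before the next patients are dosed

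*Combined protocol and SAP*

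**What the plan says.** **The gate.** Section 9 sets the rule: "If seven or more patients are deemed a success by meeting all of the criteria below", HIVM is called feasible. It continues: "If HIVM is deemed feasible, then an additional 20 patients will be accrued to this study". The four success criteria are all imaging measurements. The Synopsis also opens Part II on feasibility only.

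**The board.** Section 8: "The DSMB will review the study annually and will make recommendations". Safety data are within its remit. The section names no start for the annual clock, no Part I review and no ad hoc trigger.

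**The pace.** Section 9: "The accrual rate is estimated at one subject per month, and the estimated study duration is 30 months".

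**Reporting between reviews.** The one report with a 24-hour limit (Section 7.3.2) covers "SAEs that are serious, unexpected and for which there is a reasonable possibility that the study drug caused the adverse event" and goes to the CRS Compliance Office. Section 7.2.2 asks for an SAE form but states neither deadline nor recipient. Section 11.1 says only that serious events are handled in an expedited way. Section 12.2 lets the sponsor stop at once for safety, without naming a trigger.

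**The concern.** The step from 10 to 30 patients is the one planned decision point in the study, and harm plays no part in it. A patient who has a serious dye reaction after imaging is complete still counts as a success. If the first scheduled DSMB review comes after that step, Part II patients are dosed before the board has seen any Part I safety data.

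Between reviews the board depends on being told, and nothing in the protocol says it will be. What is at stake is whether a serious reaction attributed to a dye reaches independent reviewers before further patients receive the same dyes.

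**Working it through.** **Inputs.** Part I has 10 patients, Part II has 20, and accrual is 1 per month (Section 9). Review is annual (Section 8). The start of the annual clock is not given; I assume first enrolment and then vary it.

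**The plan's own figure.** 30 subjects / 1 per month = 30 months, which matches the stated duration.

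**Timing at the planned rate.** With accrual rate r, patient n is enrolled by month n/r.
- Part I is full at 10/1 = month 10.
- By month 12, 12 × 1 = 12 patients are enrolled, of whom 12 − 10 = 2 are in Part II.
- Later reviews are 12 patients apart, or 12/30 = 40% of the sample.

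**How far the timing can move.**

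| Change from the base case | Part I full (month) | First review (month) | Part II patients before review |
|---|---|---|---|
| none | 10 | 12 | 2 |
| r = 0.75 | 13.3 | 12 | 0 |
| r = 10/12 = 0.83 | 12 | 12 | 0 (break-even) |
| r = 1.25 | 8 | 12 | 5 |
| r = 1.5 | 6.7 | 12 | 8 |
| 2 subjects replaced | 12 | 12 | 0 (break-even) |
| 3 subjects replaced | 13 | 12 | 0 |
| clock starts 2 months before enrolment | 10 | 10 | 0 (break-even) |
| clock starts 3 months before enrolment | 10 | 9 | 0 |

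If enrolments by month 12 are Poisson with mean 12, the probability that at least 10 have been enrolled by then is 0.76.

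**The reporting route, which does not depend on timing.**
- Section 7.3.2 requires an event to be serious, unexpected and possibly caused by the study drug. Its recipient is CRS Compliance, so even a qualifying event is not sent to the board.
- Section 7.1.1 judges unexpectedness against the risk information already on file. For fluorescein, Section 1.2.2 lists anaphylaxis, bronchospasm and cardiac arrest among its severe reactions, and Appendix A adds "Rare cases of death due to anaphylaxis have been reported". For ICG, Section 1.4.2 names anaphylactic reactions, hypotension, hemodynamic instability and death. A reaction listed for the dye in question can therefore be classed as expected.
- Section 7.3.1 defines unexpectedness more widely, by kind, severity or frequency. The same event can be expected under 7.1.1 and unexpected under 7.3.1, and the protocol does not say which definition governs.
- No other section names the DSMB as a recipient of SAEs.

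**What a look at 10 patients can show.** Section 9 plans one-sided 95% Clopper-Pearson upper limits. With 0 events in 10 the limit is 1 − 0.05^(1/10) = 25.9%. A Part I review would thus serve to judge individual events; it could not establish a low reaction rate.

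**The case against.** The strongest case against is proportionality. These are single administrations of approved diagnostic dyes under anesthesia, with continuous monitoring, in at most 30 patients at one center. The protocol's own rates are low: 0.05% severe reactions for ICG, and just over 1% of any grade for fluorescein in the recent study it cites (5–10% historically). Keeping a feasibility gate separate from safety oversight is a legitimate design choice. This limits the weight of the point but does not supply the missing route to the board. The board's charter is not among the documents, so whether it allows ad hoc review is unknown.

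Four stronger readings are tempting, and the documents do not support them.

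- **The first review necessarily follows Part I.** The margin is two months and rests on estimated accrual and an assumed clock start.
- **Three severe reactions in ten would still open Part II.** Section 9 alone tolerates three failures, but the Synopsis describes stopping when the objective is not met in three or more patients, which leaves at most two. The event is also remote: at a 1% rate, the probability of three or more in ten is about 0.0001.
- **Listed reactions are shut out of the 24-hour report.** Section 7.3.1 may bring them in, because a severe reaction in so small a study can be unexpected in frequency. Bronchospasm and cardiac arrest are listed for fluorescein only, so if attributed to ICG they would count as unexpected under 7.1.1.
- **Nobody outside the study team sees the events.** All adverse events of every grade enter the database, data management reviews them, CRS Compliance receives qualifying reports, and the sponsor can terminate. What is missing is a scheduled independent review at the gate and a stated route to the board.

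**Conclusion.** The point holds in a limited form. On the documents alone, Part II opens without a safety criterion or a DSMB step, and no text sends an SAE to the board between annual reviews. Both statements stand whatever the accrual.

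The timing is conditional. At one subject per month, with the clock starting at first enrolment, about 2 Part II patients precede the first review. This fails if accrual is below about 0.83 per month, if three or more subjects are replaced, or if the clock starts more than 2 months before first enrolment; at the exact thresholds review and Part I completion coincide.

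A severe reaction listed for the dye given can miss the 24-hour report, but need not. Nothing here affects the validity of the feasibility estimate. I would treat this as a cheap improvement to oversight.

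**What to change.** 1. **Sections 8 and 9.** Time one DSMB review to the tenth evaluable Part I patient. Use data through that patient's post-operative visit (2–3 weeks, Section 6.3), and forward any later SAE within the 30-day collection window (Section 7.2.1). Make Part II conditional on both the feasibility count and a DSMB recommendation to continue. Annual reviews then follow.
2. **Sections 7.2.2 and 7.3.2.** Send SAEs judged possibly, probably or definitely related to either dye or to the imaging procedure to CRS Compliance and to the DSMB within the existing 24 hours, regardless of expectedness. Leave any pause in enrolment to the board. An automatic hold could recur often after CRS-HIPEC, because a rating of possible requires little more than plausible timing.
3. **Sections 7.1.1 and 7.3.1.** Align the two definitions of unexpected.
4. **Synopsis and Section 9.** Reconcile the stop at three or more patients with the seven-or-more rule, since the two disagree at exactly three failures.

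The cost is a short amendment, a pause of a few weeks between parts, and some extra expedited forms. There would be more than a few forms if many post-operative SAEs are rated possible. Sample size and endpoints do not change.
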